8.3.2.2. Reasons for Temporary Discontinuation of SC Study Drug

Study drug dosing will be temporarily discontinued in the event of:

• Clinically important laboratory abnormalities such as:

Regeneron Pharmaceuticals, Inc.

CONFIDENTIAL

Page 63 of 118

- Neutrophil count $<1.5 \times 10^3/\mu L$ but $>0.5 \times 10^3/\mu L$
- ALT or AST $3 \times ULN$ but $\leq 5 \times ULN$
- Platelet count $\leq 100 \times 10^{3}/\mu L$ but $> 50 \times 10^{3}/\mu L$
- Creatinine phosphokinase (CPK) >2.5 x ULN
- Serum creatinine >1.5 x ULN
- Eosinophils >5000/ μ L
- Severe laboratory abnormalities (as noted in Section 8.3.2.1) where a causal relationship to dupilumab can be reasonably excluded (ie, an alternative cause is evident). In these cases, study treatment will be discontinued while the clinical circumstances are being assessed but it may be resumed when the laboratory parameters normalize sufficiently. A decision to resume treatment will be made jointly by the investigator and medical monitor
- Other intercurrent illnesses or major surgery
- An infection that requires parenteral treatment with antibiotic, antifungal, antiviral, antiparasitic, or antiprotozoal agents, or requires oral treatment with such agents for longer than 2 weeks

After the condition leading to suspension of dosing normalizes sufficiently, study treatment may resume at the discretion of the principal investigator in consultation with the medical monitor. A decision to discontinue study drug and/or to reinstitute study treatment should be discussed with the medical monitor. Note that dosing may NOT be resumed if subject met conditions for permanently discontinuing study drug described in Section 8.3. The investigator may suspend study treatment at any time, even without consultation with the medical monitor, if the urgency of the situation requires immediate action and if this is determined to be in the subject's best interest. However, the medical monitor should be contacted as soon as possible in any case of study drug discontinuation. Resumption of study treatment after temporary discontinuation should always be discussed with the medical monitor.

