11.4.4.2. Other Safety

Vital Signs

Vital signs (temperature, pulse, blood pressure, and respiration rate) will be summarized by baseline and change from baseline to each scheduled assessment time with descriptive statistics.

CONFIDENTIAL

Page 98 of 118

The number and percentage of subjects with a treatment-emergent potentially clinically significant value (PCSV) will be summarized for each vital sign variable. The criteria for treatment-emergent PCSV will be defined in the SAP.

Laboratory Tests

Laboratory test results will be summarized by baseline and change from baseline to each scheduled assessment time with descriptive statistics.

Number and percentage of subjects with a treatment-emergent PCSV at any post-randomization time point will be summarized for each clinical laboratory test. The criteria for treatment-emergent PCSVs will be defined in the SAP.

Shift tables based on baseline normal/abnormal and other tabular and graphical methods may be used to present the results for laboratory tests of interest.

Listings will be provided with flags indicating the out of laboratory range values.

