11.5. Additional Statistical Data Handling Conventions

The following analysis and data conventions will be followed:

Definition of baseline:

• The baseline assessment will be the latest, valid pre-first-dose assessment available.

General rules for handling missing data:

• Rules for handling missing data for assessment (other than efficacy)

CONFIDENTIAL

Page 100 of 118

- If the start date of an AE or concomitant medication is incomplete or missing, it will be assumed to have occurred on or after the intake of study medication, except if an incomplete date (eg, month and year) clearly indicates that the event started prior to treatment. If the partial date indicates the same month or year of the intake of study medication date, then the start date by the study medication intake date will be imputed; otherwise, the missing day or month by the first day or the first month will be imputed.
- No imputations for missing laboratory data, vital sign data, or physical examination data will be made.

Visit windows:

• Assessments taken outside of protocol allowable windows will be displayed according to the case report form (CRF) assessment recorded by the investigator.

Unscheduled assessments:

• Extra assessments (laboratory data or vital signs associated with nonprotocol clinical visits or obtained in the course of investigating or managing AEs) will be included in listings, but not summaries. If more than 1 laboratory value is available for a given visit, the first observation will be used in summaries, and all observations will be presented in listings.

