5.7. Analysis of Safety Data

The analysis of safety and tolerability will be performed on the SAF and SAF-maintenance for each study period, as defined in Section 3.3.

The safety analysis will be based on the reported AEs, clinical laboratory evaluations, physical examination, vital signs and spirometry.

Thresholds for treatment-emergent Potential Clinically Significant Values (PCSV) in laboratory variables and vital signs are defined in Section 10.3. Treatment-emergent PCSV is any PCSV developed or worsened in severity compared to the baseline during the treatment and follow-up period.

The time interval to detect any event or abnormality is between the first injection of study medication and EOS.

The summary of safety results will be presented for each study period by treatment received in the corresponding period. For safety variables/summaries involving baseline values, e.g., absolute change from baseline or shift table, study period specific baselines will be used. Summaries for pre-dosing period and up-dosing period will use the study baseline (i.e., the latest available valid measurement prior to the first dose of study drug in the study). Summaries for maintenance period and follow-up period will use study baseline and visit 16 baseline (i.e., the last available valid measurement prior to the first dose of study drug in the maintenance period), respectively.

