6.4. Visit Windows

Data analyzed by-visit-analysis (including efficacy, laboratory data, vital sign and spirometry/PEF) will be summarized by the study scheduled visits described in the study protocol and SAP, "Schedule of Event". The analysis visit windows will be exhaustive so that all available values obtained from unscheduled visits and early termination (ET) visit have the potential to be summarized.

No analysis visit windows will be applied for the study scheduled visits.

CONFIDENTIAL

Page 56 of 86

The following analysis visit windows will be used to map the unscheduled visits and ET visit, based on the study day:

| Visit | Target Day (TD) | Analysis Time Window Based on Study Day ^a |
|---------------------------|--|---|
| Screening 1 | -113 to -17 | -113 to -17 |
| Screening 1a | -57 to -15 | -57 to -15 |
| Baseline | 1 | 1 |
| Visit 3 (Week 2) | 15 | [2, 22] |
| Visit 4 (Week 4) | 29 | [23, 36] |
| Visit 5 (Week 6) | 43 | [37, 50] |
| Visit 6 (Week 8) | 57 | [51, 64] |
| Visit 7 (Week 10) | 71 | [65, 78] |
| Visit 8 (Week 12) | 85 | [79, 92] |
| Visit 9 (Week 14) | 99 | [93, 106] |
| Visit 10 (Week 16) | 113 | [107, 120] |
| Visit 11 (Week 18) | 127 | [121, 134] |
| Visit 12 (Week 20) | 141 | [135, 148] |
| Visit 13 (Week 22) | 155 | [149, 162] |
| Visit 14 (Week 24) | 169 | [163, 176] |
| Visit 15 (Week 26) | 183 | [177, 190] |
| Following visit 15 | a – 15f are optional visits ^b during | up-dosing period |
| Visit 15a (Week 28) | 197 | [191, 204] |
| Visit 15b (Week 30) | 211 | [205, 218] |
| Visit 15c (Week 32) | 225 | [219, 232] |
| Visit 15d (Week 34) | 239 | [233, 246] |
| Visit 15e (Week 36) | 253 | [247, 260] |
| Visit 15f (Week 38) | 267 | [261, 274] |
| Following windows only ap | ply to subjects who entered doubl | e-blind maintenance period |
| Visit 16 (Week 28 to 40) | Target Day (TD) at last visit during up-dosing period ^c + 14 days | [Visit 16 TD ^d - 8 days, Visit 16 TD + 30 days] |
| Visit 17 (V16 + 4 weeks) | Visit 16 TD + 28 days | [Visit 17 TD – 13 days, Visit 17 TD + 14 days] |

| Visit 18 (V16 + 8 weeks) | Visit 16 TD + 56 days | [Visit 18 TD – 13 days, Visit 18 TD + 14 days] |
|---|---|---|
| Visit 19 (V16 + 12 weeks) | Visit 16 TD + 84 days | [Visit 19 TD – 13 days, Visit 19 TD + 14 days] |
| Visit 20 (V16 + 16 weeks) | Visit 16 TD + 112 days | [Visit 20 TD – 13 days, Visit 20 TD + 14 days] |
| Visit 21 (V16 + 20 weeks) | Visit 16 TD + 140 days | [Visit 21 TD – 13 days, Visit 21 TD + 14 days] |

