| Visit 22 (Week 52 to 64, V16 + 24 weeks) | Visit 16 TD + 168 days | [Visit 22 TD – 13 days, Visit 22 TD + 14 days] |
| Following window | ws apply to subjects who entered | follow-up period |
| Visit 23 (V16 + 28 weeks) | Target Day (TD) at last visit in pre-dosing/up- dosing/maintenance period ^e + 28 days | [Visit 23 TD – 13 days, Visit 23 TD + 14 days] |
| Visit 24 (V16 + 32 weeks) | Target Day (TD) at last visit in pre-dosing/up- dosing/maintenance period + 56 days | [Visit 24 TD – 13 days, Visit 24 TD + 14 days] |
| Visit 25 (Week 64 to 76, V16 + 36 weeks) | Target Day (TD) at last visit in pre-dosing/up- dosing/maintenance period + 84 days | ≥ Visit 24 TD + 14 days |

^a Study day is calculated relative to the date of first study drug injection.

^b Visit 15a – 15f are optional visits in order to reach 300 mg/day AR101 for at least two weeks. Subjects may reach 300 mg/day AR101 for at least two weeks at any of the optional visits.

^c The last visit during up-dosing period could be any of visit 15, 15a, 15b, 15c, 15d, 15e, or 15f.

^dVisit 16 target day (TD) is defined as target day at last visit during up-dosing period + 14 days.

^e The target day at last visit in pre-dosing/up-dosing/maintenance period could be any of the following visit: 1) visit 15 during up-dosing period; 2) ET visit during up-dosing period; 3) visit 22 during maintenance period; 4) ET visit during maintenance period.

In general, the following order will be used to select the record for analysis at given visit:

- 4. Scheduled visit
- 5. ET or end of study (EOS), whichever comes first if scheduled visit not available
- 6. Unscheduled visit if both scheduled visit and ET/EOT/EOS are not available

For the multiple measurements of the same test in the same window, the following rules will be used to select the analysis value:

- If multiple valid values of a variable within an analysis visit window, the closest from the target study day will be selected.
- If the difference is a tie, the value after the targeted study day will be selected.
- If multiple available values of a variable exist within a same day, then the first value of the day will be selected.

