| Eosinophils (EOS) | (>0.5 Giga/L and >ULN) and (\leq 0.5 Giga/L or \leq ULN at baseline) | Harrison- Principles of internal Medicine 17th Ed., 2008. |
| Hemoglobin (HGB) | ${<}100$ g/L and ${\geq}100$ g/L at baseline or any decrease ${\geq}~20$ g/L | Two criteria are independent |
| | >200 g/L and \leq 200 g/L at baseline | |
| Hematocrit (HCT) | $<0.37 \text{ v/v} \text{ and } \ge 0.37 \text{ v/v} \text{ at baseline for Male;}$ | Two criteria are independent |
| | $<0.33 \text{ v/v}$ and $\ge 0.33 \text{ v/v}$ at baseline for Female | |
| | >0.52 v/v and ≤0.52 v/v at baseline for Male; >0.47 v/v and ≤0.47 v/v at baseline for Female | |
| Platelets (PLAT) | <100 Giga/L and ≥100 Giga/L at baseline >700 Giga/L and ≤700 Giga/L at baseline | International Consensus meeting on drug- induced blood cytopenias, 1991. Two independent criteria |
| Urinalysis | | |
| pH (PH) | <5 or >7 | |
| Ketones (KETONES) Ketonuria | Presence and absence at baseline | Semi-quantitative methods |
| Ketonuna | | |

| Glucose (GLUC) Glycosuria | Presence and absence at baseline | Semi-quantitative methods |
|---|--|---|
| Erythrocytes (RBC) Microscopic Hematuria | > 5 RBCs/ HPF and ≤5 RBCs/ HPF at baseline | Semi-quantitative methods |
| Protein (PROT) Proteinuria | \geq 1+ and <1 at baseline | Semi-quantitative methods, $\geq 1+$ means concentration ≥ 30 mg/dL |
| Vital Signs | | |
| HR | ≤50 bpm and decrease from baseline ≥20 bpm ≥120 bpm and increase from baseline≥20 bpm | To be applied for all positions (including missing) except STANDING. |
| SBP | ≤90 mmHg and decrease from baseline ≥20mmHg ≥119 mmHg and increase from baseline ≥20 mmHg. | |
| DBP | ≤54 mmHg and decrease from baseline ≥10 mmHg ≥78 mmHg and increase from baseline ≥10 mmHg | |
| Temperature | Rectal, Tympanic: >100.4 °F/38.0 °C Oral: >99.5 °F/37.5 °C Axillary or skink infrared (temporal): >37.2 °C | |
| Respiratory rate | < 12 per minute and ≥12 per minute at baseline >20 per minute and ≤20 per minute at baseline | |
| Weight | ≥5 % weight loss from baseline ≥5 % weight gain from baseline | Based on identification of trends in the child's growth with a series of visits WHO Multicentre Reference Study Group, 2006; Center for Disease Control. Growth chart 2007. |

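### PCSV tables: it is unresolved which values are counted, the single eosinophil tier cannot show worsening, and the weight-gain limit takes no account of growth

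*Protocol*

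**What the plan says.** **Which values count.** Protocol 11.4.4.2 states: "Number and percentage of subjects with a treatment-emergent PCSV at any post-randomization time point will be summarized for each clinical laboratory test". Protocol 11.5 states that extra laboratory and vital-sign values "obtained in the course of investigating or managing AEs) will be included in listings, but not summaries", and that where a visit has more than one laboratory value the first is summarized. SAP 6.4 makes the analysis windows exhaustive so that "all available values obtained from unscheduled visits and early termination (ET) visit have the potential to be summarized". It then ranks the records available at a visit, with this in last place: "Unscheduled visit if both scheduled visit and ET/EOT/EOS are not available". Within a window it takes the value closest to the target day. SAP 5.7 adds: "The time interval to detect any event or abnormality is between the first injection of study medication and EOS". SAP 1.2.3, which lists departures from the protocol, does not mention the subject.

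**Eosinophils.** SAP 10.3 has a single criterion: post-baseline ">0.5 Giga/L and >ULN", together with a baseline at or below 0.5 Giga/L or at or below the upper limit of normal (ULN). SAP 5.7 defines a treatment-emergent PCSV more widely, as one that is new or has become more severe than at baseline. Protocol 8.3.2.2 lists "Eosinophils >5000" per µL among the reasons for temporarily stopping the injections.

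**Weight.** SAP 10.3 flags a loss of 5% or more, and "≥5 % weight gain from baseline". The comment beside the row refers to growth trends over repeated visits.

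**The concern.** The PCSV tables are where a reader compares the arms for extreme laboratory and vital-sign results, so they should contain each subject's worst value.

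Protocol 9.2.3.4 requires significantly abnormal results to be repeated, and such repeats are typically unscheduled. If the convention in Protocol 11.5 or the ranking in SAP 6.4 is carried over to PCSV counts, a repeat that is worse than the scheduled value is lost. Two programmers working from these documents could produce different tables.

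The eosinophil row has a different weakness. Its baseline condition removes the subjects who start high, and no higher tier exists in which they could be counted as worse. The weight row has the opposite fault: a fixed percentage in children aged 6 to 17 years counts ordinary growth as an abnormality.

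**Working it through.** **1. Unscheduled values.** The plan gives no figure to reproduce, so the rules are set against the visit schedule.

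- Hematology is scheduled at visits 4, 8 and 12 among visits 3 to 15 (Protocol Table 3). That leaves 13 − 3 = 10 of 13 windows with no scheduled value.
- Under Protocol 11.5, an extra value is excluded from summaries in all 13 windows.
- Under the SAP 6.4 ranking, an extra value is usable in 10 windows and displaced in 3.
- The 3 windows are the ones in which a prompt repeat falls. Visit 8 has target day 85 and window days 79 to 92. A repeat on days 86 to 92 of an abnormal day-85 result shares that window, and the scheduled value is kept. The subject is still counted if the scheduled value met the criterion; what is lost is a repeat that alone meets it, or meets a higher tier.
- If every post-baseline value is counted, as Protocol 11.4.4.2 and SAP 5.7 suggest, nothing is lost.

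**2. Eosinophils.** Let B be baseline and P a later value, in Giga/L. The rule is: flag if (P > 0.5 and P > ULN) and (B ≤ 0.5 or B ≤ ULN). The second bracket fails only when B > 0.5 and B > ULN, and P then has no effect. Unit check: 5000/µL = 5.0 Giga/L. The documents give no ULN, so values of 0.4 to 0.7 are assumed.

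| ULN | B | Flagged at P of |
|---|---|---|
| 0.4 | 0.45 | 0.6 and all higher values tried |
| 0.4 | 0.55 | none, up to 20 |
| 0.5 | 0.8 | none, up to 20 |
| 0.6 | 0.55 | 0.8 and all higher values tried |
| 0.7 | 0.8 | none, up to 20 |

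A rise from 0.8 to 20 Giga/L, four times the 5.0 level, is not counted. The blind spot covers the pre-dosing, up-dosing and maintenance summaries, which use the study baseline; follow-up summaries use the visit 16 baseline (SAP 5.7). ALT and AST, by contrast, each have four tiers with separate baseline conditions. The second PCSV summary in SAP 5.7.3, restricted to subjects not meeting the criterion at baseline, changes the denominator and does not recover these subjects.

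**3. Weight.** The annual gain that reaches 5% by week w is 5 × 52 / w percent, assuming linear growth.

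- Week 28: 9.3%. Week 52: 5.0%. Week 64: 4.1%. Week 76: 3.4%.
- In kilograms by week 64 (0.05 × weight × 52 / 64): 0.8 kg/year at 20 kg, 1.2 at 30 kg, 2.0 at 50 kg and 2.8 at 70 kg.
- Weeks to a flag at g kg/year: 0.05 × weight / g × 52. The documents give no growth rate. Assuming 1 to 5 kg/year, the range is 52 down to 10 weeks at 20 kg, 78 to 16 at 30 kg, 130 to 26 at 50 kg and 182 to 36 at 70 kg.
- At 2 kg/year, a child of up to about 49 kg is flagged by week 64 (2 × 64 / 52 / 0.05 = 49.2).

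Study duration is 64 to 76 weeks for those entering maintenance. The comparison with study baseline runs to visit 22, at week 52 to 64; follow-up restarts from visit 16.

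**The case against.** The best defence on unscheduled values is that the SAP 6.4 ranking is written for by-visit analyses. SAP 5.7.3 attaches by-visit wording to the descriptive statistics and not to the PCSV counts, and both documents describe detection over the whole period. On that reading the plan already counts everything. This is a reasonable reading, but neither document states it, and Protocol 11.5 says the contrary about summaries without an exception for PCSVs. A reader might infer that unscheduled tests are shut out of the tables altogether. SAP 6.4 does not support that, since it admits them in 10 of the 13 windows examined.

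On eosinophils, a large rise would still be visible elsewhere: in listings, change-from-baseline summaries and, if it came from a summarized record, the by-visit maximum. It could also be reported as an adverse event under Protocol 10.4.5. This is true, and it limits the harm. It does not give a count of subjects who worsened by arm, which is what SAP 5.7 promises. Shift tables are optional and would show such a subject as abnormal at both times.

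On weight, the rule is the same in both arms, heavier or slow-growing adolescents may never reach the limit, and loss of 5% or more is flagged separately. All of that stands.

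**Conclusion.** Three points hold, in descending order of weight.

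- The eosinophil row contradicts SAP 5.7 for subjects above both limits at study baseline, and it can miss values above the protocol's own 5000/µL level. A reader might infer that any child with raised eosinophils is beyond detection. That is wrong: a subject above only one limit can still be flagged. The number affected cannot be given, because the documents report neither the baseline distribution nor the laboratory's ULN.
- The source of values for PCSV counts is an unreconciled contradiction between Protocol 11.5, Protocol 11.4.4.2 and SAP 6.4. The worst value is lost only if the restrictive rules are applied to those counts.
- The weight-gain limit will flag many children who are growing normally. How many depends on the assumed growth rate. A reader might expect nearly every child to be flagged, but at 1 kg/year a 50 kg child needs 130 weeks. Nor do the documents make this row their means of detecting eosinophilic esophagitis: Protocol 6.1.2.5 relies on symptom solicitation at every visit, with a questionnaire and specialist referral for specified subjects. The row adds background flags equally to both arms and so blurs the comparison without favouring either.

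These are descriptive safety tables. No efficacy endpoint or hypothesis test is affected.

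**What to change.** - In SAP 5.7.3 and 5.7.4, state that PCSV counts and any worst-value shifts use all post-baseline values: scheduled, unscheduled and early termination. Keep the existing exclusion in 5.7.4 of post-dose up-dosing and food-challenge vital signs. Confine window selection to by-visit statistics, and list the change from Protocol 11.5 in SAP 1.2.3.
- In SAP 10.3, add at least one higher eosinophil tier with its own baseline condition, for example above 5.0 Giga/L with baseline at or below 5.0, following the ALT and AST rows. With that tier, a rise from 0.8 to 5.1 is counted. A rise from 0.8 to 4.9 would still need an intermediate tier, whose level the sponsor should choose. This alters the analysis table only and leaves the dosing rule untouched.
- Consider reporting change in weight-for-age z-score beside the percentage limits, with one named growth reference. The current row cites two sources and does not say which applies.

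The cost is a few sentences of SAP text, one or more table rows and some programming before database lock. No new data are needed: weight, age and sex are already collected.

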11.6. Statistical Considerations Surrounding the Premature Termination of a Study

If the study is terminated prematurely, only those parameters required for the development program and/or reporting to regulatory authorities will be summarized. Investigator and sponsor responsibilities surrounding the premature termination of a study are presented in Section 17.1.

12. DATA MANAGEMENT AND ELECTRONIC SYSTEMS

12.1. Data Management

A data management plan specifying all relevant aspects of data processing for the study (including data validation, cleaning, correcting, releasing) will be maintained and stored at Regeneron.

A medical coding plan will specify the processes and the dictionary used for coding. All data coding (eg, AEs, baseline findings, medication, medical history/surgical history) will be done using internationally recognized and accepted dictionaries.

The CRF data for this study will be collected with an EDC tool.

12.2. Electronic Systems

Electronic systems that may be used to process and/or collect data in this study will include the following:

- IWRS system randomization, study drug supply
- EDC system data capture
- E-diary
- Statistical Analysis Software (SAS) statistical review and analysis
- Pharmacovigilance safety database
- AWARE, Business Objects XI pharmacovigilance activities (Sanofi)

13. STUDY MONITORING

13.1. Monitoring of Study Sites

The study monitor and/or designee (eg, contract research organization monitor) will visit each site prior to enrollment of the first subject, and periodically during the study. Remote monitoring may be used if applicable.

